## SUMMARY OF CHANGES:

Protocol Version 1.2  
July 13, 2016:

Section 4.1 Exclusion Criteria: Updated to allow continued low-dose (81 mg daily) aspirin therapy.

Section 2, 6.1, 6.2, Table 1: Updated to move quantitative sensory testing to the screening visit, rather than baseline visit.

Section 2: Corrected to indicate that nerve conduction studies are done at the screening visit.

Section 2, 4.1, 6.1, 7.1.2: Updated to indicate that the ulnar nerve will be tested, rather than median nerve.

Protocol Version 1.3  
October 19th, 2016:

Table 1: Proposed visit schedule corrected for spelling and timing of events.

Section 1 & 10.1: Corrected to indicate that this is a single center (not multi-center) study.

Section 4.1: Added history of keloid scarring to list of exclusions.

Section 6.2: Removed language related to subject medication log

Section 10.6: Added reference that MICHR will provide study monitoring.

Throughout protocol provided clarification that research pharmacy used is Belmar Pharmacy (not UMHS Research Pharmacy).

Minor typographical, spelling and grammatical errors fixed throughout.

Protocol Version 1.4  
December 6th 2016

Section 3: Added that randomization will be by gender as well as by HbA1c.

Section 4.1: Clarified inclusion and exclusion criteria as follows;

-Severe hypoglycemia is defined by hypoglycemia resulting in coma or seizure.

-Active Hepatitis C is an exclusion.

-Active foot ulcers are an exclusion.

-Exclusion related to DKA clarified to a history of recurrent DKA or any DKA in the prior 3 months.

-Lithium use added to list of exclusions

-Upper age for eligibility increased from 65 to 70 years.

Protocol Version 1.5  
February 28, 2017

Section 4.1: Inclusion criteria amended follows;

-Inclusion criteria # 4 amended to include provision to use peroneal motor nerve conduction velocity of  $\geq 35$  m/second as inclusion criteria if sural nerve amplitude is 0  $\mu$ V (unrecordable).

Section 4.1: Clarified exclusion criteria as follows;

-Exclusion # 9 clarified with addition of chronic immunosuppressive therapy to long-term glucocorticoid therapy, exception specified for those using steroid inhalers for asthma management.

-Exclusion # 15 corrected to reflect treatment period of 12 months rather than 24 months.

-Exclusion # 16 added (exclusions related to hypersensitivity to salsalate, aspirin and other NSAIDS). Language related to hypersensitivity is

included in section 9.3 of protocol, but has now been added to the exclusion list for clarity.

-added language indicating that people with known hypersensitivity to lidocaine or epinephrine may not be able to participate as these agents are used for local anesthesia during skin biopsies.

Protocol Version 1.6  
May 01, 2017

Section 4.1: Clarified exclusion criteria as follows;

- Exclusion # 6 clarified to include “lung” transplant to match ICD

Section 5.2.3 and 6.2: Revised study drug titration schedule.

Section 9.3: Added language re: increased risk for fluid retention and edema to be consistent with risks for NSAIDs that are listed in the Salsalate package insert.

Protocol Version 1.7  
August 10, 2017

Section 3: Trial Design. Amended to reflect increased enrollment to 70 subjects and to modify randomization distribution from 1:1 (Salsalate:Placebo) to 3:2 (Salsalate:Placebo).

Section 5.1: Removed reference to 1:1 randomization ratio.

Throughout:

-Reference to enrollment of 60 subjects changed to 70 subjects

-Reference to salsalate dose clarified from “3 grams per day” to “up to 3 grams per day” to better reflect intent to use a lower dose for participants who experience dose-dependent, treatment related side effects.

-Clarified the randomization stratification by A1c from < 8% to >8% to ≤ 8.0% to >8.0%.

Protocol Version 1.8  
December 4th, 2017

Table 1: Amended to increase the allowable visit window between screening (visit 1) and baseline (visit 2)

Section 6.1: Amended last paragraph to reflect increase in allowable duration between screening (visit 1) and baseline (visit 2).

Throughout: Minor formatting changes and spelling/grammar corrections.

Protocol Version 1.9

July 11th, 2019

Section 2.0: Sudoscan removed from study procedures due to the bankruptcy of the manufacturing company and the subsequent inability to obtain supplies

Section 4.1: Clarified exclusion criteria as follows;

- Amputation Exclusion - edited exclusion criteria to allow patients who have had a lower limb amputation from a cause other than neuropathy
- Cancer Exclusion - edited exclusion criteria to only exclude patients with active cancer (other than basal cell or squamous cell skin cancer) rather than also excluding those who have had it in the last five years.
- Macroalbuminuria Exclusion - clarify that a history of persistent macroalbuminuria is checked by random urine microalbumin creatinine ratio rather than a 24-hour test.

Section 5.3: Pill Disposal - edited the method of pill disposal in the protocol such that the pills will be disposed of in a U of M pharmaceutical black bin upon patient return and pill counting, rather than returning them to Belmar.

Section 3.0 and 10.1: Changed single center to multi-site to reflect the addition of Henry Ford Health System as a performance site. In section 10.1, it is also noted that the previous version of this protocol contained an error that stated that the purpose of this single center study was the justify the conduction of single center study. This should have stated that the purpose of this single center study was the justify the conduction of multi-center study. Thus, this has now been edited to acknowledge that this is now a multi-site study that would justify a larger multi-site study.

Protocol Version 2.0  
December 16th, 2019

Table 1: Proposed Visit Schedule for TINSAL-T1DN Study: Removed Sudomotor testing row that was missed in the changes made for protocol version 1.9.

Section 6.2: Removed Sudomotor testing from visit 2 tests as that was missed in the changes made for protocol version 1.9.

Section 6.3: Removed Sudomotor testing from visit 7 tests as that was missed in the changes made for protocol version 1.9.

Protocol Version 2.1  
December 18th 2020

Hold over reference to 1:1 randomization changed to 3:2 on page 3.

Protocol TINSAL-T1DN  
Protocol 2.3 September, 2022

Section 8.8.1 updated to reflect SAE reporting in accordance with current IRB reporting guidelines.

Table one updated to reflect that visits 3-7 windows are based on medication start following visit 2 due to the shipping of the medication from Belmar pharmacy directly to the participant.

Protocol Version 2.2  
January 11, 2022

Section 6 was updated to include option for conducting visit number 4 (3 months) and 6 (9 months) remotely.

Table one updated to include a footnote indicating that visit number 4 and number 6 may be conducted remotely.

Protocol Version 2.3  
September 19, 2022

Appendix A was added. Appendix A provides a contingency plan in case of disruption to supplies of medication (salsalate or placebo)

**Table 1: Proposed Visit Schedule for TINSAL-T1DN Study**

Visit Number	Visit 1	Visit 2	Visit 3	Visit 4**	Visit 5	Visit 6**	Visit 7
Visit Description	Screening	Baseline	Monitoring	Monitoring	Monitoring/ Outcomes	Monitoring	Monitoring/ Outcomes
Time point	Day -180 to 0	Day 0	Month 1	Month 3	Month 6	Month 9	Month 12
Visit window		NA	± 7 days	± 14 days	± 14 days	± 14 days	± 14 days
Informed Consent	X						
Medical History /Physical Examination†	X	X		X	X	X	X
Laboratory Measures*	X			X	X	X	X
Skin Biopsies (proximal/distal leg)		X					X
Neurological History /Physical Examination†	X						X
Nerve Conduction Studies	X						X
Neuropathy Total Symptom Score	X	X			X		X
Cardiovascular Autonomic Studies		X					X
Resting Heart Rate		X	X	X	X	X	X
Quantitative Sensory Testing	X						X
NeuroQOL		X			X		X
Survey of Autonomic Symptoms		X			X		X
Neuropathy Pain Scale		X			X		X
Functional Assessments							
Berg Balance Scale							
8-foot Get Up and Go Test		X					
Modified Falls Efficacy Scale							X
Medication Dispensing§		X		X	X	X	
Medication Compliance			X	X	X	X	X
Medication Return				X	X	X	X
Adverse Events Monitoring		X	X	X	X	X	X

† Baseline history and examination will include diabetes duration, diabetes complications, diabetes treatment, concurrent medical problems, relevant past surgical history, height, weight, blood pressure and pulse, and foot examination. Follow up visits will include changes in medical or surgical history, weight, blood pressure, pulse and foot examination \* HbA1c, Metabolic Comprehensive Panel, Complete Blood Count with Platelets, TSH, Lipid Profile, Cystatin-C, Uric Acid and Urine Albumin performed at screening visit (unless results for these tests are documented in the medical record as being done in the prior 3 months for all except HbA1c (1 month) and Urine Albumin (6 months). Urine pregnancy test at screening for all women of childbearing potential regardless of contraceptive practiced. HbA1c, Metabolic Comprehensive Panel, CBCP, Cystatin-C, Uric Acid and Urine Albumin will be repeated at 3, 6, 9 and 12 months of follow-up. Lipids will be repeated at 3, 6 and 12 months of follow-up. Luminex inflammatory marker assays on blood and urine performed at screening or baseline, and again at study end.

\*Visit windows for visit 3-7 are based off when the patient starts the study medication following visit 2 due to the shipping of the medication from Belmar Pharmacy directly to the participant.

\*\* Visits 4 and 6 may be conducted remotely with laboratory samples collected at a Michigan Medicine affiliated lab.

§Medication dispensing, and return may be modified if study drug supplies (salsalate, placebo) are disrupted (Appendix A).

## 1. INTRODUCTION

For patients with type 1 diabetes (T1DM) and diabetic neuropathy (DN), no disease modifying treatment other than glycemic control is available. The IKK $\beta$ /NF- $\kappa$ B pathway is unique in that it is implicated in both the pathogenesis of nerve fiber loss, pain and other symptoms in DN . This will be the first study to confirm beneficial effects of the anti-inflammatory agent, salsalate, on preventing DN progression and on DN pain. The proposed study design employs a quantifiable early measure of DN, intraepidermal nerve fiber density (IENFD) of the thigh, allowing for accurate assessment of actual nerve fiber density over time, while also incorporating traditional large fiber DN outcomes, the Diabetes Control and Complications Trial/Epidemiology of Diabetes Interventions and Complications (DCCT/EDIC) primary DN endpoint , measures of pain and quality of life.

### 1.1. Background

Diabetic neuropathy is the most common chronic complication of diabetes, ultimately affecting half of patients with T1DM and leading to severe morbidity, high mortality, major physical disability, poor quality of life ; and estimated total annual costs of \$22 billion ([www.diabetes.org](http://www.diabetes.org)). Due to the complex structure and anatomy of the peripheral nervous system, DN presents with a very broad spectrum of clinical symptoms and deficits, including severe pain, sensory deficits, foot ulcers and amputations. Despite the high morbidity associated with DN, most randomized clinical trials evaluating therapies for established DN have been disappointing. To date there is no pathogenetic treatment for this condition . The Diabetes Control and Complications Trial (DCCT) demonstrated that intensive control designed to achieve near-normal glycemia is essential in reducing the risk of DN development in type 1 diabetes . However, attainable intensive glycemic control, although necessary, is insufficient to prevent adverse nervous system effects , justifying a therapeutic need to identify new drug targets to treat DN early in its course.

### 1.2. Rationale

Evidence for an important role of low-grade inflammation and of nuclear factor kappa B (NF- $\kappa$ B) activation in the pathogenesis of DN and in the pain syndrome associated with DN is emerging from both experimental  and clinical studies . This suggests that agents with known anti-inflammatory properties, such as salicylates, may prevent the development of DN and the pain associated with DN. Salsalate, a pro-drug form of salicylate, is indicated for relief of the signs and symptoms of rheumatoid arthritis, osteoarthritis and related rheumatic disorder. It is a highly effective drug in blocking the IKK $\beta$ /NF- $\kappa$ B pathway, and can be obtained at a low cost. Salsalate has recently been shown to have glucose lowering effects.

The recently published NIDDK-funded “Targeting Inflammation Using Salsalate in Type 2 Diabetes (TINSAL-T2D)” trial confirmed salutary effects of 3.5 gram/day salsalate on markers of inflammation, glucose control and overall safety after 48 weeks in patients with type 2 diabetes (T2DM).

Our initial NIDDK funded R03 (DK 094499) grant confirmed the safety and feasibility of targeting inflammation with salsalate treatment in T1DM subjects with DN (26). Our current study builds upon and expands our initial promising results and will either confirm or refute the therapeutic efficacy of salsalate in a larger T1DM cohort.

Traditionally the diagnosis of DN is made by the presence of abnormal nerve conductions (NC), and a combination of symptoms and signs of distal sensorimotor polyneuropathy. However, NC studies assess only large myelinated nerve fiber function and in early DN, these conventional measures can be normal and if abnormal, change slowly. Recent data have also described minimal worsening  or improvement in NC  in placebo and epidemiological cohorts with little relation to other measures of small fiber nerve function in diabetic patients. This was further confirmed by the relative modest changes in all NC studies in the DCCT/EDIC cohort during 13-14 years of follow-up while adhering to current standard of care .

In T1DM, DN is a diffuse, symmetrical injury to the entire peripheral nervous system (5, 30-33). The smallest A $\delta$  thinly-myelinated fibers and the unmyelinated C-fibers are likely the earliest to undergo damage in the natural history of DN. These fibers mediate pain, temperature discrimination, touch and autonomic responses, and constitute 80% to 90% of all peripheral nerve fibers (34). Current evidence on DN natural history point to a progressive course leading to later stage phenotypes that include abnormality in the morphology and function of larger nerve fibers (as documented by changes in NC studies).

Therefore, when studying a population with earlier stages of disease *which would be most amenable to a therapeutic intervention*, it is important to utilize outcome measures that best identify these patients (in this case a measure that sensitively capture small fiber deficits).

IENFD is endorsed by several societies and authorities in the field including the Toronto Consensus Panel on Diabetic Neuropathy as a reliable, efficient and valid outcome measure to assess early neuropathy in clinical trials . IENFD, is a continuous measure of small fiber neuropathy, with high positive and negative predictive values along with a high diagnostic efficiency in differentiating between subjects with and without neuropathy . The morphometric quantification of IENFD, most commonly expressed as the number of IENFs per length of section (IENF/mm e.g. density) is possible with skin biopsy, a minimally invasive procedure, with less than 1% of mild adverse events such as bleeding, swelling or erythema. Inter-observer variability for the assessment of IENFD demonstrates good agreement, especially with assessment at the thigh, and a large normative data base was recently created by an international consortium . Patient refusal rate for this procedure is minimal (less than 2 % in several past and ongoing trials of the two Principal Investigators).

## 2. TRIAL OUTCOMES

**Primary outcome:** Change from baseline to month 12 in the intraepidermal nerve fiber density (IENFD) at the distal thigh.

**Secondary outcomes:**

IENFD at the ankle at baseline and 12 months

Electrophysiological measures

- *Nerve Conduction Studies* of the sural, peroneal, and ulnar nerves will be obtained at screening and 12 months
- *Quantitative Sensory Testing*: Cold and Vibration thresholds are assessed at screening and 12 months.

- *Measures of CAN* will comprise cardiovascular reflex testing using the DCCT/EDIC protocol (R-R interval ratio during deep breathing, postural change, and Valsalva).

Clinical measures of DN will be assessed at baseline and 12 months and will include:

- a) *DN symptoms* as evaluated by the *Neuropathy Total Symptom Score-6 (NTSS-6)*
- b) *Survey of Autonomic Symptoms (SAS)*
- c) *The DCCT/EDIC Structured Neurological Examination*

Measures of DN- specific pain will include the pain domain part of the *NeuroQOL* and the *Neuropathic Pain Scale* that will be administered at baseline, 6, and 12 months.

Functional scales will be assessed at baseline and 12 months and include:

- a) *The Berg Balance Scale* which measures balance in 14 separate activities of daily living such as going from sitting-to-stand and standing on one leg; the unipedal stance portion that had been shown to be particularly reflective of neuropathy-related mobility loss;
- b) *The 8 Foot Up and Go Test*, a test of functional mobility that assesses the time needed for a subject to arise from sitting position, walk 8 ft. and turn 180 degrees around a cone and return sitting;
- c) *The Modified Falls Efficacy Scale* assessing patient's self-reported ability to perform activities of daily living (e.g. get dressed/ undressed, walking, shopping).

Quality of life measures will be administered at baseline, 6, and 12 months and include *the NeuroQOL*, a validated measure of quality of life specific to peripheral neuropathy.

**Exploratory outcomes:** will be assessed at baseline and 12 months and include:

- a) Assessment of expression of *pain-related molecules in distal leg skin biopsies*, including the ion channel TRPV1, TrkA receptors, and neuropeptides, e.g. substance P and CGRP, using our published protocol;
- b) *skin nerve fiber inflammatory markers* including TNF $\alpha$ , IL1 $\beta$ , CD68c, using our published protocol; and
- c) a complex panel of serum inflammatory markers using the Luminex 200 platform (Luminex Corporation, Austin, TX) and Millipore multiplex immunoassay panels (Millipore Corporation, Chicago, IL, which offers customization of 40 different cytokines including TNF $\alpha$ , sTNF receptor, IL1 $\beta$ , IL6, MCP-1, adiponectin, IL8, IL17, m-CSF, sVCAM-1, s-ICAM-1, IL10; and
- d) urine inflammatory markers using the Luminex 200 platform which offers customization for urinary cytokines as outlined above

### 3. TRIAL DESIGN

This is a phase II-III, multi-site randomized, double-blind, placebo-controlled clinical trial to evaluate the effect of salsalate on measures of small fiber neuropathy in 70 subjects with T1DM and mild DN. In the original study design we proposed to randomize up to 60 subjects in a 1:1 fashion to up to 3 grams of salsalate or matched placebo. In August 2017 the protocol was modified by recommendation of the DSMB to address differential study medication discontinuation rates and to increase the number of subjects exposed to study drug. Specifically, the protocol will enroll up to 70 subjects and randomize them in a 3:2 fashion to

salsalate or placebo. All subjects enrolled subsequent to the approval of the revised protocol will be randomized in 3:2 fashion, up to 3 grams per day of salsalate or placebo respectively. Treatment duration will be 12 months. Randomization will be stratified by baseline HbA1c ( $\leq 8.0$  or  $> 8.0\%$ ) and by gender within the HbA1c groups. Subjects will be evaluated every 3 months for a total of 12 months.

#### **4. STUDY POPULATION**

70 subjects with type 1 diabetes mellitus (T1DM) will be enrolled in this study.

This clinical trial can fulfill its objectives only if appropriate subjects are enrolled. The following eligibility criteria are designed to select subjects for whom protocol treatment is considered appropriate. All relevant medical and non-medical conditions should be taken into consideration when deciding whether this protocol is suitable for a particular subject.

##### **4.1. Inclusion Criteria**

1. T1DM;
2. age 18-70;
3. mild DN as defined by symptoms and/or signs, confirmed by at least one abnormality in electrophysiology studies (abnormality of at least one attribute among conduction velocity, latency, amplitude or F-Wave in at least one nerve among sural sensory, ulnar sensory, or peroneal motor);
4. sural nerve amplitude  $> 0 \mu\text{V}$ . If sural nerve amplitude is  $0 \mu\text{V}$  (unrecordable) peroneal motor nerve conduction velocity must be  $\geq 35 \text{ m/second}^*$ ;
5. on a stable insulin regimen for the 3 months prior to enrollment;
6. be willing and capable of signing the IRB approved consent form and willing and able to cooperate with the medical procedures for the study duration;
7. be willing to accept random treatment assignment to salsalate or placebo; and
8. women of childbearing age agree to use an appropriate contraceptive method (hormonal, IUD, or diaphragm) for the duration of the study and must have a negative urine pregnancy test at screening.

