### **6.1. Recruitment/Screening**

#### Visit 1: Screening/Eligibility

An eligibility visit will be scheduled for subjects who, based on preliminary screening (telephone, email, medical chart review) meet the general entry criteria (age, T1DM, diabetes duration, symptomatic peripheral neuropathy, no contraindications for salsalate, etc.). At visit 1 the investigator or her designee will obtain written informed consent, after which all required eligibility examinations will be performed. The eligibility examination will include the following laboratory assessments: HbA1c, metabolic comprehensive panel (METCOMP), complete blood count with platelets (CBCP), thyroid stimulating hormone (TSH), lipid profile, cystatin-C, uric acid, urine albumin assessment, and in all women of child bearing age and potential, a urine

pregnancy test, even if an accepted method of contraception is being used. If any of the required laboratory measures are documented in the subject's medical record as being completed in the prior 3 months (1 month for HbA1c, and 6 months for urine albumin), they will not need to be repeated at the screening visit. Additional blood and urine will be obtained for Luminex assays of inflammatory markers. The Luminex assays though may be postponed until the baseline examination.

Weight, height and seated blood pressure and pulse will be obtained.

A structured neurologic history and physical examination and nerve conduction studies will be performed at the screening visit to verify and document the presence of signs or symptoms of peripheral neuropathy, the presence of a sural nerve response, and abnormality of at least one abnormal nerve attribute (amplitude, latency, conduction velocity or f-wave) in the sural, peroneal or ulnar nerve. In the absence of a sural nerve response (e.g., sural amplitude is 0  $\mu$ V, response is unobtainable, then the presence of a peroneal motor nerve conduction velocity of  $\geq$  35 meters per second will be required for inclusion. Quantitative sensory testing will also be conducted at the screening visit.

All visit 1 measures are ideally to be completed within a 4-week time frame but may take up to 6 months (180 days) if repeated measures are needed, and may be done at one, or over several visits if that is more convenient for the subject.

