## 6.2. Baseline

### Visit 2: Baseline (Day 0).

The key activities of the baseline visit are to obtain the initial skin biopsies and to initiate treatment with either Salsalate or placebo. Cardiovascular autonomic neuropathy (CAN) assessment, as well as quality of life and symptom questionnaires, and a short battery of functional assessments, will also be performed at the baseline visit. Two skin biopsies are obtained; one at the proximal thigh, and one at the distal leg. These will be done on the subjects' dominant side unless contraindicated (e.g., presence of a cast).

Upon satisfactory completion of all eligibility and baseline assessments, including the skin biopsy, a 3 month + 14-day supply of Salsalate or placebo will be provided, and written instructions for use of the medication reviewed with and provided to the subject. Subjects will be instructed to take one tablet with breakfast for the first four days beginning with the first breakfast after receipt of the study medication. The study medication dose will be increased slowly to the maximum tolerated dose (2 tablets, 3 times daily) using the following schedule: Beginning on day 5, take 1 tablet with breakfast and 1 tablet with lunch. Beginning on day 9, take 1 tablet at breakfast, 1 tablet at lunch, 1 tablet at dinner. Beginning on day 23, take 2 tablets at breakfast, 1 tablet at lunch, 1 tablet at dinner. Beginning on day 27 take 2 tablets at breakfast, 2 tablets at lunch, 1 tablet at dinner. The maximum dose of study medication, 2 tablets at breakfast, 2 tablets at lunch, and 2 tablets at dinner, may be started no sooner than the 31st day from receiving the first supply of study medication.

Subjects are to be reminded to return any unused study medication at their next visit.

Study staff will contact the subject within one week of the baseline visit to assess medication compliance and tolerance and to inquire as to the status of the biopsy sites.

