Salsalate is not approved for use in pregnant or nursing women. Pregnant and nursing women (and women who are planning pregnancy) are excluded from participation. Subjects are asked about current contraceptive practices during screening and those with child-bearing potential must agree to use an acceptable form of contraception during the study [oral contraceptive pills, injectable contraception (e.g. depo-provera) IUDs, barrier contraceptives (diaphragm/condoms), or surgical contraception (tubal ligation)]. A urine pregnancy test will be performed on all women of childbearing potential at baseline, regardless of contraceptive practices and will be repeated during the study if indicated. Women who suspect pregnancy are asked to contact the study staff and may be asked to have a pregnancy test. Women who suspect pregnancy or who are known to be pregnant are instructed to stop study medication immediately and to contact the study staff.

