### **1. New subject enrollment**

Enrollment of new subjects (Screening Visit 1) may be paused until the investigator is notified that adequate supplies of study medications are available. Eligible participants who have not yet completed Visit 2 (randomization, assignment, and initiation of study medication) will have Visit 2 postponed. The protocol currently allows for Visit 2 to take place up to 180 days after Visit 1. If Visit 2 must be delayed for more than 180 days due to unavailability of study medication, then baseline laboratory measures performed at Visit 1 will be repeated at Visit 2. A delay of over 365 days would require that all Visit 1 screening measures be repeated prior to Visit 2. Reconsent of the participant would be required in this case.

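### No pregnancy test is scheduled at Visit 2 before drug release; the only clearly scheduled mandatory test is at screening, up to 180 days earlier, and Section 9.3 is ambiguous on the timing

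*Combined protocol and SAP*

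**What the plan says.** Section 4.1, inclusion criterion 8, asks women to use contraception "for the duration of the study and must have a negative urine pregnancy test at screening". The Table 1 footnote has the same timing: "Urine pregnancy test at screening for all women of childbearing potential regardless of contraceptive practiced". Section 6.1 lists the test among the Visit 1 eligibility laboratory assessments.

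Table 1 places Visit 1 anywhere from Day -180 to Day 0. Section 6.1 gives 4 weeks as the ideal for completing the Visit 1 measures, but they "may take up to 6 months (180 days) if repeated measures are needed, and may be done at one, or over several visits". Appendix A, part 1, confirms the outer limit: "The protocol currently allows for Visit 2 to take place up to 180 days after Visit 1".

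Section 6.2 describes Visit 2 (Day 0): skin biopsies, autonomic testing, questionnaires, functional tests and the start of study drug, with a supply of 3 months plus 14 days. It lists no pregnancy test, and the laboratory row of Table 1 has no mark at Visit 2. In Section 6.3, testing at Months 3, 6, 9 and 12 is left to the investigator.

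Section 9.3 reads differently: "A urine pregnancy test will be performed on all women of childbearing potential at baseline, regardless of contraceptive practices", and the test "will be repeated during the study if indicated".

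**The concern.** Pregnancy is an exclusion (exclusion criterion 5), and Section 9.3 states that salsalate is not approved in pregnancy. The pregnancy test on which eligibility rests may nevertheless be months old when drug is released. A woman who conceives after a negative screening test, and who does not suspect it at Visit 2, could be randomized and supplied by a site that has followed inclusion 8, Table 1 and Section 6.2 exactly.

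The wording of Section 9.3 adds to the difficulty. A coordinator working from the visit schedule and an investigator working from the risk section could reach different conclusions about whether a Day 0 test is required. At stake are the safety of a few participants and a single clear instruction to sites.

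**Working it through.** **1. Where each place puts the test**

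| Place | Timing | Mandatory? |
|---|---|---|
| 4.1, inclusion 8 | Screening | Yes |
| Table 1 footnote | Screening | Yes |
| 6.1 | Screening (Visit 1) | Yes |
| 6.2 and Table 1, Visit 2 | None listed | - |
| 6.3, Months 3, 6, 9, 12 | At those visits | Investigator's discretion |
| 9.3 | *Baseline*, then if indicated | Yes, then conditional |

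**2. What *baseline* means in Section 9.3**

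For Day 0: it is the title of Visit 2, and the preceding sentence of 9.3 says contraceptive practice is asked about during screening, as if the two occasions differ.

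For Visit 1: baseline HbA1c is the stratification factor (Sections 3, 5.1) and a covariate (10.2), yet HbA1c is drawn at screening. Section 2 places the structured neurological examination at baseline, and Table 1 puts it at screening. Appendix A, part 1, calls the Visit 1 laboratory measures baseline measures.

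Both readings can be defended. If 9.3 means Day 0, the schedule omits a required test. If it means screening, the documents agree with each other but no mandatory test falls at Visit 2.

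**3. Length of the gap**

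The maximum scheduled gap is 180 days. The 4-week ideal is for completing the Visit 1 measures; I take it as the target gap. Because Visit 1 may be spread over several visits, the pregnancy test need not fall on its first day. Appendix A has Visit 1 laboratory measures repeated at Visit 2 only when a drug shortage delays Visit 2 beyond 180 days, and it does not name the pregnancy test. Section 6.1 accepts chart results from the prior 3 months for required laboratory measures. Whether that covers the pregnancy test is not stated; if it does, the gap could exceed 180 days.

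**4. Expected number of women**

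The protocol gives no figure to reproduce. The inputs below are assumptions, not in the documents:
- N, women of childbearing potential among the 70 subjects: 20 (10 to 30).
- r, pregnancy rate on contraception per year: 5% (1% to 10%).
- w, days of conceptions too late for the screening test but test-positive and unrecognised at Day 0: 42 (28 to 56).

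For w, assume a test turns positive about 14 days after conception and pregnancy is recognised by about 56 days. Then w = min(gap, 56 - 14) = min(gap, 42). This gives 28 at a 4-week gap and 42 at any gap of 6 weeks or more; 56 is a wider alternative.

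Expected women = N × [1 - (1 - r)^(w/365)].

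Central: 1 - 0.95^(42/365) = 0.588% per woman; 20 × 0.00588 = 0.118.

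| Case | Expected women |
|---|---|
| Central (N=20, r=5%, w=42) | 0.118 |
| w=28 (4-week target) | 0.079 |
| w=56 | 0.157 |
| N=10 / N=30 | 0.059 / 0.177 |
| r=1% / r=10% | 0.023 / 0.241 |
| All low (N=10, r=1%, w=28) | 0.008 |
| All high (N=30, r=10%, w=56) | 0.48 |

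Varying one input at a time gives 0.02 to 0.24; varying all together gives about 0.01 to 0.5.

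Subjects enrolled before the August 2017 revision were randomized 1:1 and later ones 3:2 (Section 3), so the salsalate share lies between 50% and 60%. Centrally that is 0.118 × 0.5 = 0.059 to 0.118 × 0.6 = 0.071 women on active drug.

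**The case against.** The strongest reply is that *baseline* in Section 9.3 simply means the screening test. The protocol uses the word that way for HbA1c, the neurological examination and the Visit 1 laboratory measures. On that reading inclusion 8, Table 1, Section 6.1 and Section 9.3 all agree, and what remains is a preference for a second test.

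The plan also has other safeguards: required contraception, exclusion of intended pregnancy, eligibility confirmed before randomization (Section 5.1), history and examination at Visit 2, contact within one week, a Month 1 visit, slow titration, and a stop rule: "Women who suspect pregnancy or who are known to be pregnant are instructed to stop study medication immediately". Section 6.1 aims for 4 weeks and allows 180 days only where measures must be repeated.

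Much of this stands. A reader might infer that Section 9.3 promises a Day 0 test which the schedule then breaks. The documents do not support that as an established contradiction, because the word is used both ways. A reader might also take 180 days as the usual gap; it is only the outer limit.

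The reply does not remove the gap itself. None of the listed safeguards is a mandatory test at Visit 2, and the stop rule acts only once pregnancy is suspected or known.

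**Conclusion.** The concern holds as a low-severity gap in patient safety. The only clearly scheduled mandatory test is at screening, and none is scheduled at Visit 2 before drug release. That is true whichever way Section 9.3 is read, and its wording is ambiguous enough to need correcting.

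The expected number of affected women is well under one across the assumed ranges, whose inputs all come from outside the documents. Nobody should infer an effect on power, type I error or the primary analysis; nothing in the statistical design depends on this test. The case rests on the seriousness of the possible exposure and the very low cost of preventing most of it. On the detection assumption used above, a Visit 2 test would still miss conceptions in the preceding two weeks or so, so it narrows the gap without closing it entirely.

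**What to change.** Keep the screening test. Add to inclusion criterion 8, Table 1 and Section 6.2 a negative urine pregnancy test at Visit 2 for every woman of childbearing potential, done before the biopsies, randomization and release of study drug. Reword Section 9.3 to refer to the screening and Visit 2 tests by visit, in place of *baseline*.

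The cost is one urine test per such woman at a visit she already attends, and a wording amendment to four places. No visit, subject or analysis is added. The documents do not give enrolment status; if enrolment has finished, only the wording correction remains useful.
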